7.1.2.2.4 SVC

The slow vital capacity (SVC) is the volume of air expired through an unforced maneuver measured by spirometry. SVC of 50% or greater of estimated measure is required to participate in the study.

7.1.2.2.5. The Columbia-Suicide Severity Rating Scale (C-SSRS)

Suicidal ideation and behavior will be prospectively assessed during this study using the Columbia Suicide Severity Rating Scale (C-SSRS). The C-SSRS will be administered by trained raters at specified time points, as indicated in the Trial Flow Chart, as well as at unscheduled visits as clinically indicated. Site staff will review the contents of the C-SSRS for completeness. Note that the C-SSRS assessment is not considered complete until all available sources of information have been considered (e.g., subject input may be necessary).

The C-SSRS is not explicit about whether the subject specifically has ideation at the time of screening. If a subject reports a prior history of ideation/behavior, the assessor will also inquire and document if this is also present at the time of the screening visit.

Subjects who at any time during this trial report suicidal ideation or behavior that is considered to be an adverse event, either between visits or during visit interviews, must be assessed by the Investigator. Subjects who report suicidal ideation with intent, with or without a plan or method (i.e., a positive response to items 4 or 5 in the assessment of suicidal ideation on the C-SSRS) or suicidal behavior must be evaluated that day by a

psychiatrist or other trained mental health professional who is a licensed psychologist, social worker, or mental health nurse practitioner (or comparable professional qualification in countries outside the United States). Only subjects whose suicidal ideation is passive, who expressly deny any intent to act, and who, after evaluation, are not judged to be at serious risk for self-harm during the trial may continue in the study; others must be discontinued from trial participation and receive appropriate clinical follow-up care to ensure their safety. In addition, any reports of 1) suicidal behavior; 2) suicidal ideation with intent, with or without a plan or method; or 3) suicidal ideation considered to be a clinically significant change, including all cases of suicidal ideation that are treatment- emergent (i.e., start or worsen after trial treatment is initiated) must be recorded as an Event of Clinical Interest (See Section 7.2.3.2). Sites will designate which health care professionals are to be responsible for acute care on-site and to specify referral center(s) to be used for further evaluation. The C-SSRS will be completed in paper form, and will be scored by the qualified trained rater, via a subject interview.

7.1.3 Laboratory Procedures/Assessments

7.1.3.1. Neurofilaments light (NfL) levels in plasma

Plasma NfLs has been validated as outcomes for ALS trials, based on tofersen approval by FDA³⁴. At the designed visits, blood will be collected, plasma will be extracted and frozen until its use. Plasma NfL will be measured by Simoa at baseline, after each stimulation session and by end of the DBP and end of the OLE.

7.1.3.2. Biomarkers in nEVs

Extracellular vesicles of neuronal origin (nEVs) is a promising strategy to identify new biomarkers. Such vesicles can be isolated from plasma (even frozen plasma) and reflects the cytoplasm content of the neuronal population 12h in advance. The vesicles content is representative of the cytoplasm and includes proteins, RNAs and metabolites. Then, nEVs can be considered as a surrogate approach to a liquid biopsy of the brain. As such, several biomarkers have been identified in patients with ALS²⁶, Alzheimer disease^{27, 28}, Parkinson disease^{29, 30}, traumatic brain injury or MS³¹. Here, we propose collecting nEVs to conduct a biomarker search study to identify biomarkers associated with the TPS therapy in the motor cortex of people with ALS.

Multiple protein related with the pathogenesis of ALS or CNS damage (SOD1, Ataxin 2, C90rf72, UNC13A, TDP43, stathmin 2, NfL and NfH levels) has been proposed as biomarkers of ALS³⁹. However, their levels required a lumbar tap, reducing their feasibility. The use of extracellular vesicles of neuronal origin will allow to determine such proteins reflecting the neurons cytoplasmatic content 12h before²⁶. 20 ml of blood will be collected at the designated visits (5 visits = 100 ml in total) and plasma and serum will be collected and stored at -80C until analysis (no DNA will be collected). Protein levels will be measured by SIMOA, MSD or WES at [name]'s lab.

7.1.4 Other Procedures

7.1.4.1 Withdrawal/Discontinuation

When a subject discontinues/withdraws from participation in the trial during visit 2 (before completing the three planned stimulations), all applicable activities scheduled for the end of visit 2, as outlined in Section 6.0 Trial Flow Chart, will be performed at the time of

discontinuation. Any adverse events which are present at the time of discontinuation/withdrawal will be followed in accordance with the safety requirements outlined in Section 7.2 - Assessing and Recording Adverse Events

7.1.4.2 Blinding/Unblinding

When the investigator or sub-investigator needs to identify the treatment arm used by a subject in case of emergency e.g., the occurrence of serious adverse experiences, he/she will contact the emergency unblinding call center by telephone and make a request for emergency unblinding. As requested by the investigator or sub-investigator the emergency unblinding call center will provide the information to him/her promptly and report unblinding. The emergency unblinding call center will make a record promptly however, the investigator or sub-investigator must enter the intensity of the adverse experiences observed, their relation to study arm, the reason thereof, etc., in the medical chart etc., before unblinding is performed. Additionally, the investigator must go into the IVRS system and perform the unblind in the IVRS system to update arm disposition. If the emergency unblinding call center is not available for a given site in this trial, IVRS/IWRS should be used for emergency unblinding in the event that this is required for subject safety.

If unblinding has occurred, the circumstances around the unblinding (e.g., date and reason) must be documented promptly, and principal investigator notified as soon as possible. Only the principal investigator or delegate and the respective subject's code should be unblinded. Trial site personnel directly associated with the conduct of the trial should not be unblinded.

7.1.4.3 Domiciling

NA

7.1.4.4 Calibration of Critical Equipment

TPS device is calibrated as follows: the electromagnetic stimulator is calibrated by the vendor (Storz medical) every 2 million pulses. The distilled water of the stimulator is replaced every 6 months. The systems have no other calibration or maintenance requirements.

7.1.5 Visit Requirements

Visit requirements are outlined in Section 6.0 - Trial Flow Chart. Specific procedure-related details are provided above in Section 7.1 - Trial Procedures.

7.1.5.1 Visits

Each visit should be performed as noted in the Trial Flow Chart. For visits that require additional explanations, please see those specific visits below.

7.1.5.1.1 Visit 1: Screening, brain MRI, TMS and SVC

At Visit 1, subjects who provide informed consent will undergo a series of diagnostic and safety assessments to determine if they are eligible for the trial. A designated subject must also consent to participate and will be asked to complete certain assessments throughout the trial. Subjects planning to undergo elective procedures during the study (known prior to trial start) should not proceed until such procedures have been completed.

At the screening visit, medical history, use of drugs, alcohol, caffeine, smoking will be recorded. In addition urine test and the Columbia-Suicide Severity Rating Scale (C-SSRS) will be administered. The SVC will be collected by spirometry.

If the subject fulfills the inclusion criteria and signs the informed consent, a brain MRI and a TMS study will be scheduled in the following 2-7 days (always before Visit 2). Once obtained the brain MRI, it will be uploaded to the TPS device for neuronavigation purposes. TMS will be conducted for defining presence of hyper-excitability.

7.1.5.1.2 Visit 2: baseline

Patients will be randomized to either treatment or sham stimulation and assigned a code (except for patient sin stage 1, which are not randomized, and all receive active stimulation). Before starting stimulation, the researcher will conduct a vital signs, physical exam and neurological examination. Urine (50 ml) and blood (20 ml) will be collected and stored. Then, the patient will be subjected to the first TPS stimulations (a 20 min stimulations).

7.1.5.1.3 Visit 3-5, 6-12, 15-21 and 22-28: stimulation visits

At each visit the patient will be reassessed for vital signs, physical exam and neurological exam. After the completion of each 6-session period, the C-SSRS will be administered. Blood and urine will be collected the last day of stimulation for each 6-session period. TMS and ALSFRS-R will be assessed the last day of stimulation for each 6-session period.

7.1.5.1.2 Visit 13, 14 and 29: end of stage 1, end of DBP, onset and end of OLE of stage 2

During such visits, vital signs, physical exam, and neurological exam and ALSFRS-R will be conducted.

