4.2.3.2 Safety Endpoints

The safety and tolerability of TPS will be continuously assessed throughout the study via Adverse Event reporting, and vital signs will be assessed at every trial visit. The Columbia-

Suicide Severity Rating Scale (C-SSRS) will be conducted at the baseline and end of the treatment to prospectively assess for the emergence of suicidal ideation and behavior.

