6.0 TRIAL FLOW CHART

Table 3 Trial flow chart

Stage 1 Visit Number	1	2	3-5	6
Visit Title	Screen	Baseline	Stimulation	End
Scheduled Week	0	1	2-3	4
Scheduling Window by Days:	3	3	2	5
Administrative Procedures				
Informed Consent	X			
Inclusion/Exclusion Criteria	X			
Identification Card	X			
Medical History	X			
Prior Medication Review	X			
Monitor Trial Device Compliance		X	X	
Clinical Procedures Assessments				
TPS stimulations	X	X	X	
Vital Signs		X	X	X
Physical Exam		X	X	X
MRC sum score		X	X	X
Hand-held dynamometry		X	X	X
Brain MRI		X		
TMS		X		
Neurological examination	X	X	X	X
C-SSRS	X	X	X	
ALSFRS-R	X	X	X	X
Blood draw		X	X	X
SVC		X		

Stage 2 Visit Number	1	2	3-5	6-7	8	9	10-16	17-18	19
Visit Title	Screen	Rand Base	Stim	Stim FU	End DBP	Onset OLE	Stim 3	Stim FU	End OLE
Scheduled Week	0	1	2-3	8-16	16	16	16-18	26-34	34
Scheduling Window by Days:	3	3	2	2	5	7	2	2	5
Administrative Procedures									
Informed Consent	X								
Inclusion/Exclusion Criteria	X								
Identification Card	X								
Medical History	X								
Prior Medication Review	X								
Monitor Trial Device Compliance		X	X	X			X	X	
Clinical Procedures Assessments									
TPS stimulations	X	X	X	X			X	X	
Vital Signs		X	X	X	X	X	X	X	X
Physical Exam		X	X	X	X	X	X	X	X
MRC sum score		X	X	X	X	X	X	X	X
Hand-held dynamometry		X	X	X	X	X	X	X	X
Brain MRI	X								
TMS	X	X	X	X	X				
Neurological examination	X	X	X	X	X	X	X	X	X
C-SSRS	X	X	X	X			X	X	
ALSFRS-R	X	X	X	X	X	X	X	X	X
Blood draw		X	X	X	X				
SVC		X				X			

Stim: TPS stimulation (6 times in 2 weeks, 20 min each); rand: randomization; Base: baseline; DBP: double blind period; OLE: Open Label Extension

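### No scheduled C-SSRS closes Stage 1, the blinded period or the open-label extension, and three protocol sections disagree on when the scale is given

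*Protocol*

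**What the plan says.** - **Purpose.** Protocol 8.4.2 and 8.6 name two kinds of safety data, adverse events and treatment-emergent suicidality. Section 8.4.2 says the C-SSRS is to capture suicidal events in a systematic, prospective way.
- **Flow chart (6.0).** The C-SSRS is marked at screening, baseline and the stimulation visits. It is blank at Stage 1 Visit 6 (End) and at Stage 2 Visits 8 (end of the double-blind period, DBP), 9 (onset of the OLE) and 19 (end of the OLE).
- **End-of-period visit text** (the block after 7.1.5.1.3, numbered 7.1.5.1.2 a second time): "During such visits, vital signs, physical exam, and neurological exam and ALSFRS-R will be conducted". The C-SSRS is not in the list.
- **Stimulation-visit text (7.1.5.1.3):** "After the completion of each 6-session period, the C-SSRS will be administered".
- **Safety endpoint rationale (4.2.3.2):** the scale "will be conducted at the baseline and end of the treatment to prospectively assess for the emergence of suicidal ideation and behavior".
- **C-SSRS section (7.1.2.2.5):** it is given at time points "as indicated in the Trial Flow Chart, as well as at unscheduled visits as clinically indicated". Ideation counts as treatment-emergent if it should "start or worsen after trial treatment is initiated".
- **Clock.** The Stage 2 chart row reads "Scheduled Week 0 1 2-3 8-16 16 16 16-18 26-34 34", which puts the end of the DBP at week 16. Section 1.0 gives a 6-month randomized phase and a month-6 primary endpoint.

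**The concern.** A safety measure that is meant to be systematic needs a reading when each observation period closes. Here none of the three periods has one. The visits are already held, and other scales, including the ALSFRS-R, are collected at them, so the omission is not forced by the schedule.

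Two things are at stake. First, suicidality that begins late in the blinded period, in either arm, may be found only if the patient volunteers it or a clinician suspects it. Second, sham patients move to active stimulation in the OLE (4.2.2.1; section 1.0 says this is offered), and one stated aim of the OLE is to add safety data. Without a reading at the changeover, ideation first found in the OLE may not be assignable to the sham period or the active period. A sham patient who declines the OLE may have no further scheduled reading at all.

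**Working it through.** The protocol states no figure of its own here. The check is to read the chart by column and then compute the gap under each schedule the document supports.

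**Reading the chart.** In both stages the C-SSRS row carries marks in exactly the same columns as the row for TPS stimulations. In the same chart ALSFRS-R, vital signs and neurological examination are marked at Stage 1 Visit 6 and Stage 2 Visits 8, 9 and 19. The end-visit text independently omits the C-SSRS, so the blanks are unlikely to be an artefact of table extraction. The visit numbers in that text (13, 14, 29) differ from the chart (8, 9, 19), so I matched the visits by title.

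**Inputs.**
- Last single blinded session: month 4 (5.2.2), or chart Visit 7, taken as week 16, the end of the printed 8-16 range.
- End of the six-session block: week 3 (chart).
- End of the DBP: week 16 (chart) or month 6 (1.0).
- One month = 365.25 / 12 / 7 = 4.348 weeks, so month 4 = 17.39 weeks and month 6 = 26.09 weeks.

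**Gap from the last scheduled blinded C-SSRS to the end of the DBP.**

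| Governing schedule | Last reading | End of DBP | Gap |
|---|---|---|---|
| Chart visits, printed weeks | week 16 | week 16 | 16 − 16 = 0 weeks, apart from visit windows |
| Chart visits, 6-month DBP, Visit 7 at week 16 | week 16 | 26.09 | 26.09 − 16 = 10.1 weeks |
| Chart visits, 6-month DBP, Visit 7 at month 4 | 17.39 | 26.09 | 26.09 − 17.39 = 8.7 weeks |
| After six-session blocks only (7.1.5.1.3), 6-month DBP | week 3 | 26.09 | 26.09 − 3 = 23.1 weeks |
| After six-session blocks only, printed weeks | week 3 | week 16 | 16 − 3 = 13 weeks |

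The six-session rule excludes the single sessions at months 2 and 4, which is why its gap is longer. Section 4.2.3.2 cannot be placed with certainty. If the end of treatment means the last stimulation, it gives the same gap as the chart. If it means the end-of-period visit, the chart does not carry it out.

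**Changeover to the OLE.** On the chart, the next reading falls somewhere in Visits 10-16 (weeks 16-18), with no order set against that day's stimulation. Under the six-session rule it follows the first OLE block. The interval from the last reading is then 26.09 + 2 − 3 = 25.1 weeks with a 6-month DBP, or 18 − 3 = 15 weeks on printed weeks.

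**The other two closings.** In Stage 1, readings stop with stimulation at week 3. That is 4 − 3 = 1 week before the charted end, but 8 − 3 = 5 weeks before the week-8 primary endpoint. At the end of the OLE, the gap on printed weeks is 0 if Visit 18 falls at week 34. Under the six-session rule it is 34 − 18 = 16 weeks.

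**The case against.** A reader might infer that suicidality arising on sham is first recorded after active OLE stimulation has begun and so counts against TPS. The documents do not support that.

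- **Other routes of capture exist.** Section 7.1.2.2.5 allows unscheduled C-SSRS, requires assessment of suicidality reported at any time, and makes treatment-emergent ideation an Event of Clinical Interest. An event can therefore be recorded before the OLE.
- **Attribution to TPS is not stated.** Treatment-emergence runs from the start of trial treatment, and 7.2 counts sham as product, so ideation that starts on sham is already treatment-emergent on sham. Start dates are recorded for adverse events (Table 4 in 7.2.4). Section 8.5.1 groups patients by treatment received but gives no rule for a patient who crosses over.
- **The blinded gap is the same in both arms.** It lowers sensitivity in each; a bias against either arm is not shown.
- **The gap may be small.** On the chart's printed weeks it is near zero. It would also be wrong to combine a last reading at month 4 (the chart) with a first OLE reading only after six sessions (7.1.5.1.3), because no single schedule gives both.
- **Section 8.4.2 sets Visit 2 as the primary safety time.**

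These points remove the directional claim and any single gap length. They do not supply the missing reading. Unscheduled assessment depends on report or suspicion, which is less than the systematic capture that 8.4.2 promises. That section also has safety data collected throughout the study. The near-zero gap rests on an end of DBP at week 16, which conflicts with the month-6 primary endpoint.

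**Conclusion.** The point holds as a gap in scheduled assessment together with an internal contradiction. No scheduled C-SSRS closes Stage 1, the blinded period or the OLE, and 4.2.3.2, 6.0 and 7.1.5.1.3 disagree on timing. With a 6-month blinded period, the last 9 to 10 weeks (chart visits) or 23 weeks (six-session rule) have no scheduled reading. On the chart's printed weeks the figure is about 0. These sizes assume that Visit 7 falls at week 16 or month 4 and that the first block ends at week 3.

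The consequence is incomplete ascertainment in both arms. In sham patients who enter the OLE, onset may also not be separable between sham and active stimulation. That group is at most 40/3, about 13, at the 2:1 ratio in section 1.0, or 40/2 = 20 at the 1:1 ratio in 5.3. These are ceilings on the patients exposed to the gap and say nothing about how many would be misclassified. Correcting the schedule is a cheap improvement, and a missed closing reading cannot be recovered later.

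**What to change.** 1. Mark the C-SSRS in the flow chart at Stage 1 Visit 6 and Stage 2 Visits 8 and 19, and add it to the end-of-period visit text.
2. State that the Visit 8 reading (or the Visit 9 reading, if both fall on the same day) is taken before the first OLE stimulation. Use it as the final blinded reading and as the baseline for emergence in the OLE.
3. Reconcile 4.2.3.2, 6.0 and 7.1.5.1.3 so that one C-SSRS schedule applies.
4. Reconcile 1.0 and 6.0 on when the blinded period ends, since this decides how long the gap is.

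The cost is a few minutes of interview at visits the patient already attends. The C-SSRS is a paper interview, and 7.1.2.2.5 already provides for trained raters.

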Measurements & Procedures	
 1. ALSFRS-R 2. SVC 3. MRC sum score 4. Hand-held Dynamometry 5. Motor cortex excitability by TMS 6. Plasma NfL levels 7. Blood: isolation nEVs and biomarker quantification (SOD1, Ataxin 2, C90rf72, UNC13A, TDP43, stathmin 2, NfL and NfH) 8. Brain MRI for neuronavigation 9. TPS stimulations (6 sessions of 20 min each in 2 weeks)
Study Product / Intervention	Neurolith is a medical device delivering transcranial pulse stimulations under neuronavigation guidance.
Controls	ALS patients allocated to sham stimulations. Sham treated patients will be offered to receive TPS therapy in the Open Label Extension phase (OLE) of the trial for ethical purposes.
Number of Participants & Rationale	
Stage 1: n=10
 
Stage 2: n=40 (randomization 2:1 active vs sham stimulation)
 
Rationale for sample size: this is an exploratory sample likely to be informative for experience in planning for future trials.

Study Duration:	
24 months
 
Stage 1: 6 months
 
Stage 2: 3 months recruitment, 6 months randomized phase, 6 months OLE, 3-month analysis and clinical scientific report

Timelines:	
Stage 1:
 
 ● First Patient First Visit (FPFV): September 1st, 2024 ● Last Patient Last Visit (LPLV): February 1st, 2025 
Stage 2:
 
 ● First Patient First Visit (FPFV): March 1st, 2025 ● Last Patient Last Visit (LPLV): October 1st, 2026
Study Schedule:	
Patients are recruited from the ALS center at Hospital del Mar from patients diagnosed with ALS and referrals provided by the local ALS foundation (Miquel Valls Foundation)
 
Stage 1: V1: informed consent, inclusion/exclusion criteria, TMS cortex excitability, brain MRI (for neuronavigation) can be conducted at any time between Visit 1 and 2; V2: stim; V3: TMS and biomarkers assessment week 4; V4: TMS and biomarkers assessment week 8.

	Stage 2: V1: informed consent, inclusion/exclusion criteria, TMS cortex excitability, brain MRI (for neuronavigation) can be conducted at any time between Visit 1 and 2; V2: randomization and baseline; V3-5: stim, biomarkers and scales; V6-V7: open label extension
Study Center:	ALS center and Neuromodulation center. Hospital del Mar – Pompeu Fabra University, Barcelona, Spain

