5.2.1 Therapeutic regimen Selection: TPS stimulation protocols

20 min stimulation with a maximum of 6,000 pulses and maximum of 0.25 mJ/mm² per session. 6 Sessions in 2 weeks per treatment period followed with a single stimulation session every 2 months (2 additional sessions by month 2 and 4).

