8.4.1. Efficacy Endpoints

Rationale for the key efficacy endpoints is given in Section 4.2.3.1 and an initial description of the efficacy measures is included in Section 7.1.2.2. In general, if a baseline value exists for a particular efficacy measure, then the change from baseline in that value will be evaluated.

Primary Endpoint

- Stage 1. Change in the motor cortex excitability threshold from baseline to week 8.
- Stage 2. Change from baseline to month 6 in the ALS functional rating scale-revised (ALSFRS-R) total score.

Secondary Endpoint

Secondary stage 1:

1. Change in the motor cortex excitability (paired-pulse transcranial magnetic stimulation (ppTMS): motor evoked potential (MEP) amplitudes, resting motor threshold, intra-cortical facilitation (ICF) and short intracortical inhibition (SICI)), from baseline to week 4
2. Change plasma NfL levels from baseline to week 4 and 8

3. Changes in muscle strength, assessed by MRC sum score from baseline to week 4 and 8
4. Changes in hand-held dynamometry from baseline to week 4 and 8

Secondary stage 2:

1. Differences (treated vs sham) and change (from baseline to end of the study (month 6)) in the slow vital capacity (SVC)
2. Differences (treated vs sham) and change (from baseline to end of the study (month 6)) in plasma NfL levels or other biomarkers from exploratory stage 1 if found significant
3. Differences (treated vs sham) and change (from baseline to end of the study (month 6)) in cortical hyperexcitability (MEP amplitudes, resting motor threshold, ICF and SICI)
4. Changes in muscle strength, assessed by MRC sum score from baseline to end of the study (month 6)
5. Changes in hand-held dynamometry, from baseline to end of the study (month 6)

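### In the Stage 2 flow chart, SVC, the first secondary endpoint, is scheduled at OLE onset and not at the end of the double-blind period, which is itself dated week 16 although the endpoints are at month 6

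*Protocol*

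**What the plan says.** **Endpoint.** Protocol 8.4.1 lists as the first Stage 2 secondary endpoint: "Differences (treated vs sham) and change (from baseline to end of the study (month 6)) in the slow vital capacity (SVC". The Trial Outline and section 3.2 agree.

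**Flow chart (6.0, Stage 2).** The nine columns are "Screen Rand Base Stim Stim FU End DBP Onset OLE Stim 3 Stim FU End OLE". The scheduled weeks of the last six are "8-16 16 16 16-18 26-34 34". End DBP (Visit 8) and Onset OLE (Visit 9) are thus both at week 16, with windows of 5 and 7 days. SVC is ticked at Visits 2 and 9 only.

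**OLE entry.** The Trial Outline says: "Sham treated patients will be offered to receive TPS therapy in the Open Label Extension phase (OLE) of the trial for ethical purposes".

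**Visit text (7.1.5).** The paragraph covering end of DBP and onset and end of OLE says: "During such visits, vital signs, physical exam, and neurological exam and ALSFRS-R will be conducted". It numbers these visits 13, 14 and 29. For the stimulation visits, 7.1.5.1.3 says "TMS and ALSFRS-R will be assessed the last day of stimulation for each 6-session period", and it times blood the same way.

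**NfL.** Section 7.1.3.1 says: "Plasma NfL will be measured by Simoa at baseline, after each stimulation session and by end of the DBP and end of the OLE".

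**Which source leads.** Sections 7.1.5 and 7.1.5.1 direct the site to the flow chart and use the visit text for visits that need further explanation.

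**The concern.** A treated-versus-sham comparison at the end of the blinded period needs its measurement at the visit that closes that period, from everyone who reaches it. Here the only follow-up SVC is attached to the entry visit of a phase the patient may decline. No SVC is charted between Visit 2 and Visit 9, so there is no intermediate value to fall back on. Spirometry also becomes harder as ALS advances, and willingness to continue may fall with it. The missing values could therefore be related to the outcome, and no analysis can recover a test that was never scheduled.

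The date matters as well. If the site follows the chart, measurements labelled month 6 will be taken at week 16. In addition, a site that tries to use the visit text beside the chart will find that the visit numbers do not correspond.

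**Working it through.** No sample-size or power figure is at issue. The check aligns the chart cells with their columns, converts the dates, and compares the chart with the text.

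**Step 1. Stage 2 chart, by column.** Every row checked has nine cells, so the alignment is consistent.

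| Row | V1 | V2 | V3-5 | V6-7 | V8 End DBP | V9 Onset OLE | V10-16 | V17-18 | V19 |
|---|---|---|---|---|---|---|---|---|---|
| Week | 0 | 1 | 2-3 | 8-16 | 16 | 16 | 16-18 | 26-34 | 34 |
| TPS | X | X | X | X | | | X | X | |
| ALSFRS-R | X | X | X | X | X | X | X | X | X |
| SVC | | X | | | | X | | | |
| TMS | X | X | X | X | X | | | | |
| Blood | | X | X | X | X | | | | |
| MRC sum score | | X | X | X | X | X | X | X | X |
| Dynamometry | | X | X | X | X | X | X | X | X |

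At Visit 8 the chart has the primary outcome and the sources of four of the five secondary endpoints. SVC is the exception.

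**Step 2. Who has a follow-up SVC?** Visit 9 has no TPS tick; OLE stimulation begins with Visits 10-16. In numbered order, the Visit 9 SVC precedes OLE stimulation and falls in the same scheduled week as Visit 8. It can serve as the end-of-DBP value for anyone who attends. A patient who attends Visit 8 and does not go on to Visit 9 has no charted post-baseline SVC. Section 7.1.4.1 does not cover this case, because its discontinuation assessments concern withdrawal during Visit 2.

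**Step 3. How many?** The Protocol gives no OLE entry rate, so the number cannot be derived. Each such patient is 1/40 = 2.5% of the randomised sample.

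**Step 4. Dates.** Month 6 = 6 × 365.25 / 12 / 7 = 26.1 weeks, and 26.1 − 16 = 10.1 weeks. Counted from Visit 2 at week 1, End DBP comes 16 − 1 = 15 weeks after baseline, and the shortfall is 26.1 − 15 = 11.1 weeks. Section 5.2.1 describes the initial course as "followed with a single stimulation session every 2 months (2 additional sessions by month 2 and 4". Month 4 is 4 × 365.25 / 12 / 7 = 17.4 weeks, so the chart closes the DBP at about the time of the last blinded session instead of two months later.

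**Step 5. Chart against visit text.**

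| Item | Chart 6.0 | Text 7.1.5 |
|---|---|---|
| End DBP, onset OLE, end OLE | Visits 8, 9, 19 | Visits 13, 14, 29 |
| TMS and blood | Visits 2 to 8 (TMS also at Visit 1), none in the OLE | last day of each 6-session period |
| Entry SVC | Visit 2 | Visit 1 |

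In the chart, numbers 13 and 14 fall inside the OLE stimulation block (Visits 10-16) and 29 does not exist. Section 7.1.3.1 agrees with the chart that NfL is measured at end of DBP, but adds an end-of-OLE measurement for which the chart has no blood draw.

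**The case against.** The strongest reply is that the SVC gap is narrow. Visits 8 and 9 share a week, no stimulation intervenes, and section 4.2.2.1 says without qualification that sham patients receive active stimulation in the OLE. A patient too ill for Visit 9 might also fail spirometry at Visit 8, so moving the tick would not recover every value. The endpoint is secondary, in a 40-patient pilot whose section 8.1 promises descriptive results only. All of this limits the size of the point. It does not remove it: the Trial Outline describes the OLE as an offer, section 5.8 lets patients withdraw at any time, and a blinded-period endpoint should not depend on either.

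Four stronger readings are tempting and are not supported.

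- *A reader might infer that the SVC value is contaminated by open-label stimulation.* In numbered order it is not, because the chart has no TPS at Visit 9.
- *A reader might infer from the visit text that none of the five secondary endpoints is measured at end of DBP.* That treats a short list as exclusive. The text never mentions MRC sum score or dynamometry at any visit and omits ALSFRS-R at baseline, so read that way it would also delete the primary endpoint's baseline. The chart governs and has four of the five at Visit 8.
- *A reader might infer that the last blinded TMS and blood samples come at about week 3-4.* This combines the regimen in 5.2.1, the timing in 7.1.5.1.3 and the chart's weeks. The visit text follows a different scheme, with stimulation visits numbered 6-12 before Visit 13, and on that scheme the samples could fall close to end of DBP.
- *A reader might put a figure on the resulting bias.* Any such figure needs an OLE non-entry rate, by arm, and its relation to decline. The document gives none of these.

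**Conclusion.** The point holds in a limited form. By the chart, one of the five Stage 2 secondary endpoints has no measurement at the visit that ends the randomised comparison. Patients who attend Visit 9 in numbered order lose nothing. Those who complete the DBP without entering the OLE have no follow-up SVC, and their number is unknown. That their loss would be related to progression is plausible in ALS, but it is an assumption.

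The week-16 date is the wider error. It places the end of the DBP 10 to 11 weeks before month 6 and affects the primary ALSFRS-R endpoint as well as the secondary ones.

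The mismatch in visit numbers and in TMS and blood timing is a clarity fault. This rests on reading 7.1.5 and 7.1.5.1 as giving the chart precedence, which is the natural reading. ALSFRS-R is scheduled at end of DBP in both chart and text, so the missing SVC tick does not touch the primary endpoint.

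**What to change.** 1. In 6.0, move the Stage 2 SVC tick from Visit 9 to Visit 8.
2. Date Visit 8 at month 6 and shift the OLE visits after it. On the chart's week count this is about week 26, or week 27 if month 6 runs from Visit 2 (1 + 26.1). Keeping the charted OLE length of 34 − 16 = 18 weeks, Visit 19 moves to about week 44 or 45.
3. Require the Visit 8 assessments (ALSFRS-R, SVC, TMS, blood, MRC sum score, dynamometry) of every randomised patient, before any OLE session and whether or not the patient enters the OLE.
4. Rewrite the end-of-DBP paragraph in 7.1.5 with the chart's visit numbers and this list.

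**Cost.** No test is added, since one spirometry moves from Visit 9 to Visit 8. All OLE visit dates shift by about 10 to 11 weeks. The stated study duration already allows for a six-month randomised phase: 6 months for Stage 1, then 3 + 6 + 6 + 3 = 18 months for Stage 2, giving the planned 24.
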